## 4.2.2. Subject Completion

A subject will be considered to have completed the study if the subject meets at least one of the following conditions:

- Subject reaches 18 years of age while in the treatment phase of the study. Study treatment should be discontinued within 3 months after the 18th birthday.
- Subject is in the treatment phase of the study at the time of local regulatory approval of eltrombopag for pediatric chronic ITP. Study treatment should be discontinued within 3 months after regulatory approval is received.

#### 5. STUDY TREATMENTS

The term 'study treatment' is used throughout the protocol to describe the product under evaluation in this protocol.

## 5.1. Eltrombopag GSK Investigational Product

#### **Eltrombopag Tablets**

Eltrombopag tablets will be white, round film coated tablets containing eltrombopag olamine equivalent to 12.5 mg, 25 mg, 50 mg and 75 mg of eltrombopag. The 12.5 mg tablet will be smaller than the 25 mg, 50 mg and 75 mg tablets.

Tablets will be packaged in white 45cc HDPE bottles with white plastic, induction-seal child-resistant caps. Each bottle will contain 35 tablets.

#### **Eltrombopag Powder for Oral Suspension**

Eltrombopag powder for oral suspension (Eltrombopag PfOS) is a reddish-brown to yellow powder contained inside an elongated sachet. Each sachet will contain eltrombopag olamine equivalent to 20 mg of eltrombopag per gram of powder.

PfOS sachets will be packaged in a carton. Each carton pack will hold 35 sachets along with a plastic reconstitution container and a syringe-adapt cap. The pack will also contain an extra syringe-adapt cap as a spare. The clinical site will provide a 10cc syringe with each carton.

Refer to Section 5.2 for the required preparation of the sachets, which is to be performed by the subject/parent/guardian prior to dosing.

## 5.1.1. Eltrombopag Dosage and Administration

For subjects between the ages of 6 to 17 years old, eltrombopag tablets will be administered, however, subjects between the ages of 6 to 11 years old may use PfOS if they have difficulty swallowing tablets and are receiving a dose of eltrombopag of < 40

mg. For subjects between the ages of 1 to 5 years old, either eltrombopag tablets or PfOS will be administered.

Any change between PfOS and tablet formulations should take into account the differences in bioavailability between formulations. In a relative bioavailability study conducted under fasted conditions in healthy adult subjects, the eltrombopag PfOS formulation delivered 22% higher plasma eltrombopag AUC( $0-\infty$ ) and 30% higher Cmax compared to the tablet formulation. When switching from PfOS to tablets, the nearest tablet strength rounding up should be used.

The maximum dose allowed will be 75 mg once daily.

Site personnel will instruct the subjects (and their parents/guardians) on how to take their medication. Every effort should be made to encourage subject compliance with the dosage regimen as per protocol.

Study treatment will be dispensed in either bottles containing 35 tablets each, or packs containing 35 unit-dose sachets each, which will be given to each subject's parents/guardians starting on Day 1.

For subjects who receive tablets, new study treatment containers (bottles) will be dispensed at each change in dose or dose frequency, and study treatment compliance will be assessed as described in Section 5.7. For subjects who receive PfOS, study treatment compliance will be assessed at each visit as described in Section 5.7, and additional packs of sachets will be dispensed when the site personnel determine the current supply will not be sufficient until the next study visit. All subjects/parents/guardians should be instructed to bring all bottles or sachets with any unused drug to each visit with the investigator.

## 5.1.2. Study Treatment Starting Dose

After completion of treatment in TRA115450, subjects will continue on the same dose during this study unless adjustments are warranted according to the dosing guidelines. For children between the ages of 1 to 11 years old, a change in formulation (between PfOS and tablets) may also be considered based upon guidelines in Section 5.1.1.

### 5.1.3. Dose Adjustment

Each subject's dose of study treatment will be adjusted as needed following the provided dosing guidelines and based upon their individual platelet response. The Investigators are allowed to use their clinical judgment in determining dose adjustments. In this study, the target platelet count range is between 50 Gi/L and 200 Gi/L. As previously stated, the goal is to have a platelet count in a safe haemostatic range, not necessarily in the normal range.

#### 5.1.3.1. General Dose Adjustment Considerations

Investigators are expected to use their clinical judgment and knowledge about each subject's individual disease characteristics (including platelet count fluctuation and response to prior doses) for any dose adjustment.

The following considerations should be taken into account when modifying the dose of study treatment. These considerations should be used in conjunction with the specific guidelines for the tablet formulation (Refer to Section 5.1.3.2), and with the specific guidelines for the suspension formulation (Refer to Section 5.1.3.3).

- 1. Changes in concomitant ITP medications that could affect the platelet count.
- 2. Other clinical situations which, in the opinion of the investigator, may affect the platelet count, **for example, among others**:
  - Subject received systemic corticosteroids for a different condition
  - A viral infection that may decrease OR increase the platelet count
- 3. Subject's response to eltrombopag during prior study participation (TRA115450). If a subject has a platelet count that would require changing the dose to a dose that was previously proven to achieve platelet counts outside of the desired range (<50 or > 200 Gi/L), alternating doses of different strength tablets or changes in frequency may be considered. For example:
  - If a subject taking 50 mg daily has a platelet count >200 Gi/L and hence requires a dose reduction, but 37.5 daily has proven to result in a platelet count below 50 Gi/L, the subject may require 50 mg and 37.5 mg doses on alternate days.
  - If a subject taking 12.5 mg daily has a platelet count <50 Gi/L and hence requires a dose increase, but 25 mg has proven to result in a platelet count > 200 Gi/L, the subject may require 12.5 mg and 25 mg on alternate days.
  - If a subject is on a 12.5 mg daily dose and has a platelet count >200 Gi/L, a dose of 12.5 mg every other day may be required (changing the frequency of dosing).

After a dose adjustment, investigators must wait at least 2 weeks before making any other adjustment, with the exception of reducing eltrombopag if the platelet count rises above 200 Gi/L and interrupting eltrombopag if the platelet count rises above 400 Gi/L.

If a subject's platelet count increases significantly and if the investigator thinks a dose reduction is medically appropriate, the dose can be decreased even if the platelet count is below 200 Gi/L or a dose modification was done less than 2 weeks before.

If after an interruption the subject's platelet count decreases drastically and if the investigator thinks re-initiation is medically appropriate, the dose can be reinitiated at the next lower dose level even if the platelet count has not yet decreased to below 150 Gi/L. (Refer to Dose Decrease guidelines in Section 5.1.3.2, below.)

If a subject's platelet count decreases drastically and the investigator thinks a dose increase is medically appropriate, the dose can be increased even if the platelet count is more than 50 Gi/L.

# 5.1.3.2. Dose Adjustment Guidelines for subjects receiving the tablet formulation

Dose adjustment guidelines for the tablet formulation are provided in the below sections and in Table 1.

#### Dose Increase

Dose increases can be made every 2 weeks until the target platelet count or the maximum allowed dose of 75 mg daily is achieved.

If a subject has a platelet count < 50 Gi/L and requires a dose increase, and the next higher dose (increase of 12.5 mg) has already proven to be associated with platelet counts > 200 Gi/L, then alternating doses may be used (e.g., 25 mg and 37.5 mg on alternating days).

#### Dose Decrease

If platelets rise above 200 Gi/L, subjects will reduce their dose by 12.5 mg at 2 week intervals until the platelet count is below 200 Gi/L. If platelets rise above 400 Gi/L, subjects will interrupt eltrombopag and platelet counts will be monitored within 1 week and every 3-4 days thereafter; once platelets are below 150 Gi/L, eltrombopag will be restarted at the next available lower dose level.

If a subject requires a dose lower than the available tablet strengths or between 2 available tablet strengths, alternate dosing regimens that modify the frequency of administration may be implemented as described in Section 5.1.3.1. Such alternate regimens must be documented in the CRF.

Table 1 Dose Adjustment Guidelines - Tablet formulation

Distalat a sunt		
Platelet count	Dose	Dose adjustment
	12.5 mg	Increase to 25 mg
	25 mg	Increase to 37.5 mg
<50 Gi/L 	37.5 mg	Increase to 50 mg
<50 Gl/L 	50 mg	Increase to 62.5 mg
	62.5 mg	Increase to 75 mg
	75 mg	Maintain 75 mg dose 
50 – 200 Gi/L	Maintain current	dose
	12.5 mg	Decrease to 12.5 mg every other day
	25 mg	Decrease to 12.5 mg
200 – 400 Gi/L 	37.5 mg	Decrease to 25 mg
200 – 400 GI/L 	50 mg	Decrease to 37.5 mg
	62.5 mg	Decrease to 50 mg
	75 mg	Decrease to 62.5 mg
		After interruption reinitiate at a reduced
	12.5 mg	frequency, 12.5 mg every other day
>400 Gi/L	25 mg	After interruption, reinitiate at 12.5 mg
Interrupt study treatment until	37.5 mg	After interruption, reinitiate at 25 mg
platelets < 150 Gi/L 	50 mg	After interruption, reinitiate at 37.5 mg
	62.5 mg	After interruption, reinitiate at 50 mg
	75 mg	After interruption, reinitiate at 62.5 mg

- If a subject has reached the maximum allowed dose and has platelet counts < 50 Gi/L, the investigator (or designee) may choose to have the subject continue in the trial if clinical benefit is documented in terms of improved platelet counts OR reduced bleeding symptoms.
- 2. If a subject requires a dose adjustment, and the next available dose (adjusting by 12.5 mg) has already proven to be associated with platelet counts outside of the target range (i.e., <50 Gi/L or >200 Gi/L), then alternating doses may be used, as described in Section 5.1.3.1.
- 3. The Investigator may consider keeping the current dose if a drop in platelet counts would be expected by reducing the dose.
- 4. If the platelet count is still above 150 Gi/L within one week after study treatment interruption, the platelet count needs to be monitored 3-4 days later, and twice a week thereafter. Once the subject's platelet count is ≤150 Gi/L, study treatment should be started at the next lower dose or frequency.

## 5.1.3.3. Dose Adjustment Guidelines for subjects receiving the suspension formulation

The starting dose of eltrombopag for subjects receiving the PfOS formulation will be the subject's last dose in TRA115450 unless an adjustment is required based on the platelet count.

The dose of eltrombopag will be increased or decreased according to platelet counts as outlined in Section 5.1.3.1. These modifications will initially be in strength intervals of 30% (rounded up) as shown in Table 2, but intermediate dosing levels may be used if the platelet response warrants it. Subsequent dose adjustments should be made based upon the current dose of eltrombopag. The starting dose and each adjusted dose will be documented in the CRF.

For a calculated dose of 18 to 24 mg, subjects should receive one sachet, which is equivalent to a 20 mg dose. A subsequent dose adjustment would be based upon the actual dose of 20 mg, i.e., a 30% increase in dose would be an increase of 6 mg for a total of 26 mg. For calculated doses of 38 to 44 mg, subjects should receive a 40 mg dose (two sachets); subsequent dose adjustment would be based on the actual dose received, i.e., 40 mg.

 Table 2
 Dose Adjustment Guidelines – suspension formulation

Weight (kg)	Initial Dose (mg)	Initial Dose (ml)	Adjust dose by  (mg)	Adjust dose by (ml)
8	10	5	3	1.5
9	11	5.5	4	2
10	12	6	4	2
11	13	6.5	4	2
12	14	7	5	2.5
13	16	8	5	2.5
14	17	8.5	6	3
15	20 	10	6	3
16	20 	10	6	3
17	20 	10	6	3
18	20 	10	6	3
19	20 	10	6	3
20	20 2	10	6	3
21	25	12.5	8	4
22	26	13	8	4
23	28	14	9	4.5
24	29	14.5	9	4.5
25	30	15	9	4.5
26	32	16	10	5
27	33	16.5	10	5
28	34	17	11	5.5
29	35	17.5	11	5.5
30	36	18	11	5.5
31	38	19	12	6
32	39	19.5	12	6
33	40	20	12	6
34	41	20.5	13	6.5
35	42	21	13	6.5
36	44	22	14	7
37	45	22.5	14	7
38	46	23	14	7
39	47	23.5	15	7.5
40	48	24	15	7.5

1. This table illustrates the doses based upon a subject's weight and the corresponding 30% dose adjustment. Subsequent dose adjustments would be calculated based upon the current dose (and not the starting dose).

2. For a calculated dose of 18 to 24 mg, subjects should receive one sachet, which is equivalent to a 20 mg dose. A

subsequent dose adjustment would be based upon the actual dose of 20 mg, i.e., a 30% increase in dose would be an increase of 6 mg for a total of 26 mg.

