#### **Eltrombopag Powder for Oral Suspension**

The powder for oral suspension PfOS is presented as a reddish brown to yellow powder, which when reconstituted with water forms a reddish-brown suspension. The sachet should not be opened until ready to use. Add 9.5 mL of water drawn using a 10cc syringe into the provided plastic container. Cut open the sachet and add the entire content of the sachet into the container with water. The container is capped and shaken for 10-20 seconds. The resulting suspension contains 2 mg/mL of eltrombopag dose. The prescribed volume (dose) is drawn through the syringe port on the cap with a syringe. Upon dosing, the rest of the remaining suspension in the container is discarded. The container and the syringe are rinsed with water and dried.

If the prescribed dose is > 24 mg, which will require that part or all of a second sachet be used, then the suspension can be prepared by adding the contents of the two sachets to 19.0 mL of water, and then following the steps outlined above. The water has to be drawn by using the 10cc syringe twice, and similarly dosing has to occur by using the same 10cc syringe twice.

A fresh dose is prepared everyday just prior to the dosing and no storage of the reconstituted suspension is allowed.

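### Suspension dosing: the 38–44 mg rounding rule and Table 2 disagree, and Protocol Section 5.2 describes no preparation above 40 mg although one 30% step from 40 mg gives 52 mg

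*Protocol*

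**What the plan says.** Protocol Section 5.1.3.3 has two rounding rules for the suspension. Calculated doses of 18–24 mg are given as one 20 mg sachet. For the upper band it says "For calculated doses of 38 to 44 mg, subjects should receive a 40 mg dose (two sachets", and adds: "subsequent dose adjustment would be based on the actual dose received, i.e., 40 mg".

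On step size the section says "These modifications will initially be in strength intervals of 30% (rounded up) as shown in Table 2", with intermediate levels allowed if the platelet response calls for them. The starting dose is the child's "last dose in TRA115450 unless an adjustment is required based on the platelet count". Footnote 1 to Table 2 reads: "This table illustrates the doses based upon a subject's weight and the corresponding 30% dose adjustment"; later steps are calculated from the current dose.

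Section 5.2 describes reconstitution of one sachet to 2 mg/mL. For prescribed doses above 24 mg, "the suspension can be prepared by adding the contents of the two sachets to 19.0 mL of water", and "dosing has to occur by using the same 10cc syringe twice". No third sachet or third draw is mentioned.

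Section 5.1.1 sets a maximum of 75 mg once daily, with no separate maximum for the suspension. Children aged 6–11 "may use PfOS if they have difficulty swallowing tablets and are receiving a dose of eltrombopag of < 40" mg. Ages 1–5 may use either formulation.

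**The concern.** There are two conflicts and one consequence.

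1. **Text against table.** The prose turns any calculated dose of 38–44 mg into 40 mg. Table 2 prints unrounded doses in that band. Because the table does apply and footnote the 18–24 mg rule, it cannot be read as simply showing doses before rounding.
2. **Titration against preparation.** The prose expects further adjustment from 40 mg, and Table 2 lists doses up to 48 mg. The preparation instructions stop at what two sachets hold.
3. **Eligibility (secondary).** At ages 6–11, a calculated 38 or 39 mg is below 40 mg as Table 2 prints it, but becomes 40 mg under the rounding text and then fails the Section 5.1.1 condition.

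Section 5.1 has the family prepare the suspension before dosing. Two sites reading the same section could give different doses for the same calculated dose and take the next step from different bases. For a dose above 44 mg, the protocol gives the caregiver no preparation step. This concerns the consistency of paediatric dosing instructions. The SAP summarises exposure by duration only, so that summary is unaffected.

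**Working it through.** **Inputs.** Doses, volumes and steps come from the 33 rows of Table 2 (8–40 kg). The step is 30% of the dose, rounded up (Section 5.1.3.3). One sachet is 20 mg (Section 5.1.3.3), the concentration is 2 mg/mL, and the syringe is 10 cc (both Section 5.2).

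**Reproducing the table.** Step = 30% × dose, rounded up to a whole mg; volume = dose ÷ 2 mg/mL. All 33 printed steps and their volumes reproduce. Examples: 10 mg → 3; 20 mg → 6; 40 mg → 12; 48 mg → 14.4, rounded up to 15. The table is therefore intact and consistent within itself. The conflict is with the surrounding text and is not a miscalculation.

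**Text against table, 38–44 mg band.** Rows in the 18–24 mg band that print anything other than 20 mg: none. Rows in the 38–44 mg band that print anything other than 40 mg: five of six (33 kg prints 40 mg).

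| Weight (kg) | Table 2 dose (mg) | Difference from 40 mg | Table 2 step (mg) | Step from 40 mg | One increase, table (mg) | One increase, text (mg) |
|---|---|---|---|---|---|---|
| 31 | 38 | −5% | 12 | 12 | 50 | 52 |
| 32 | 39 | −2.5% | 12 | 12 | 51 | 52 |
| 34 | 41 | +2.5% | 13 | 12 | 54 | 52 |
| 35 | 42 | +5% | 13 | 12 | 55 | 52 |
| 36 | 44 | +10% | 14 | 12 | 58 | 52 |

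Three steps differ: 13/12 = +8% (twice) and 14/12 = +17%. One step down gives 26, 27, 28, 29 and 30 mg from the table rows, against 40 − 12 = 28 mg from the text.

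**Preparation capacity.** Two sachets × 20 mg = 40 mg; 40 ÷ 2 = 20 mL; 2 × 10 mL = 20 mL. Sachets and syringe draws give the same ceiling.

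- From 40 mg: 40 + 12 = 52 mg; 52 ÷ 2 = 26 mL; 52 ÷ 20 = 2.6 sachets.
- Table 2 at 37–40 kg: 45, 46, 47 and 48 mg = 22.5, 23, 23.5 and 24 mL = 2.25, 2.30, 2.35 and 2.40 sachets. These lie outside both rounding bands.
- 41, 42 and 44 mg also exceed two sachets. They have a described preparation only if the rounding text overrides the table.

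So 4 of 33 rows, and any titrated dose above 44 mg, have no preparation described in the protocol under either reading.

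**How titration gets there.** With both rounding rules applied after each full 30% increase, the 29 rows at or below 44 mg first exceed 44 mg after:

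| Full increases | 1 | 2 | 3 | 4 | 5 | 6 |
|---|---|---|---|---|---|---|
| Rows | 9 | 6 | 7 | 3 | 3 | 1 |

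Examples are 34 + 11 = 45 mg (one step) and 20 → 26 → 34 → 45 mg (three steps). These count printed rows along paths the rule allows. They are neither patients nor forecasts.

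**Eligibility at ages 6–11.** 29 + 9 = 38 mg and 30 + 9 = 39 mg. Each is below 40 mg as printed and equals 40 mg after rounding.

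**The case against.** The strongest reply is that the reach is small. Table 2's initial doses are keyed to weight, but this study starts each child on the last TRA115450 dose, and the footnote calls the table illustrative. A calculated 38–44 mg therefore arises by titration or is carried over, and for that case the prose is explicit. A site would have to follow an illustrative row over a direct sentence. Doses of 40 mg or more on suspension are open only to ages 1–5, who may switch to tablets. Intermediate steps and investigator judgement are allowed, so 52 mg is the default step and not a required one. Doses are titrated to platelet counts, with weekly visits while unstable. The Study Procedures Manual may hold further preparation instructions. On the 6–11 condition, the wording about the dose being received suggests the rounded dose.

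Much of this stands as a limit on size. The eligibility point is secondary and largely follows from the first conflict. The missing preparation step can be asserted only of the protocol, since the manual is not available here. But the section also directs sites to Table 2 for the adjustments, so the table is not inert. The preparation gap does not depend on Table 2's starting doses, because the prose itself expects adjustment from 40 mg. That the above-24 mg instruction has no stated upper limit does not help: two sachets still hold only 40 mg. And Section 3 describes the manual as covering detail that does not bear on subject safety, which makes it a poor home for the only instruction on preparing a higher dose.

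**Conclusion.** The point holds as an internal inconsistency and should be fixed. Text and Table 2 disagree in 5 of 33 rows on dose (−2 to +4 mg around 40 mg) and in 3 of 33 on step size. The preparation described in Section 5.2 reaches 40 mg, while the default step from 40 mg gives 52 mg and four listed doses lie at 45–48 mg.

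This rests on the 20 mg sachet, the 2 mg/mL concentration and the 30% rounded-up step, all stated in the protocol. How many children it touches is unknown: at most 12 enrol, the number using suspension is not given, and at 40 mg or above only ages 1–5 are concerned. Sample size and planned analyses are unaffected.

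**What to change.** Reconcile three places so that they agree: the 38–44 mg rounding text, the dose and adjustment columns of Table 2, and the preparation steps in Section 5.2. Section 5.2 should either cover every suspension dose that the table and the titration rule allow, or state the limit that applies. In Section 5.1.1, state whether the below-40 mg condition for ages 6–11 refers to the calculated or the rounded dose. Which dose, step or limit is correct is for the sponsor's clinical and pharmacy team to decide.

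The cost is a wording and table correction in an amendment or a dosing clarification letter. It needs no new data item and no change to sample size or analysis.

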## 5.2. Preparation of Study Treatment

#### **Eltrombopag Tablets**

Tablets will be provided to the site and no specific preparation of study treatment is required prior to administration.

#### **Eltrombopag Powder for Oral Suspension**

The powder for oral suspension PfOS is presented as a reddish brown to yellow powder, which when reconstituted with water forms a reddish-brown suspension. The sachet should not be opened until ready to use. Add 9.5 mL of water drawn using a 10cc syringe into the provided plastic container. Cut open the sachet and add the entire content of the sachet into the container with water. The container is capped and shaken for 10-20 seconds. The resulting suspension contains 2 mg/mL of eltrombopag dose. The prescribed volume (dose) is drawn through the syringe port on the cap with a syringe. Upon dosing, the rest of the remaining suspension in the container is discarded. The container and the syringe are rinsed with water and dried.

If the prescribed dose is > 24 mg, which will require that part or all of a second sachet be used, then the suspension can be prepared by adding the contents of the two sachets to 19.0 mL of water, and then following the steps outlined above. The water has to be drawn by using the 10cc syringe twice, and similarly dosing has to occur by using the same 10cc syringe twice.

A fresh dose is prepared everyday just prior to the dosing and no storage of the reconstituted suspension is allowed.

